The use of topical agents for control of chronic GVHD manifestations is part of usual clinical care for affected patients. Common examples include various eye drops and artificial tears for ocular sicca, steroid or other immune suppressive agent mouth rinses for oral involvement, or topical steroid creams for mild cutaneous involvement. Use of these agents for patients on study will not be controlled or directed by this protocol. Rather, use of these agents will be directed by treating clinicians as part of usual clinical care. Use of these agents will be recorded in data capture on each study visit. Use of these non-systemic therapies will not inform study endpoints that include requirement for additional systemic immune suppressive therapies.

iv. Supportive antimicrobial prophylaxis on study

- i. All patients on study must receive antimicrobial prophylaxis per BMT guidelines and standards for the prevention of bacterial, viral, fungal, and pneumocystis infections.

V. STUDY OUTCOMES/ANALYSIS ENDPOINTS

1. Safety

a. Definition of DLT for phase I component:

- i. In the phase I study, dose escalation will proceed as previously described. The dose limiting toxicity (DLT) will be defined using CTCAE version 4.0 as the following:
 - Events occurring within 46 days of the last dose of drug (4 half-lives) that are:
 - a) Grade 4 infusion reactions,
 - b) Grade 4 constitutional symptoms at least possibly due to ofatumumab,
 - c) Grade 3 organ toxicities (neurologic, pulmonary, cardiac, gastrointestinal, genitourinary, hepatic, cutaneous) at least possibly due to ofatumumab,
 - d) Grade 4 neutropenia lasting more than 14 days
- ii. Importantly, known infusional toxicities of ofatumumab are managed appropriately with modification of infusion rate or temporary halting of infusion, as well as with supportive care including IV fluids, anti-histamines, and steroids.
- iii. Specifically, grade 1-3 infusion-associated adverse events defined by CTC version 4.0 are not considered DLT in this trial. The occurrence of grade 4 infusion-associated adverse event is considered DLT.
- iv. According to observed toxicities in the phase I component, the greatest dose tolerated in the dose escalation will be carried forward into the phase II component of the trial as the recommended phase II dose.
- v. Events clearly related to chronic GVHD, relapse of the primary hematological disorder, concurrent medication, or infection will not be included as a DLT.

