**cohort/dose level -1 (100mg days 0 and 14) will be pursued only if 2/3 patients in cohort 1 (300mg days 0 and 14) experience DLT.*

Phase I trial endpoint:

Safety of escalating dose of ofatumumab in combination with prednisone.

Definition of dose-limiting toxicity (DLT):

Dose-limiting toxicity attributable to ofatumumab within 46 days of initiation of ofatumumab therapy is defined in the *above section V.1 safety for definition of DLT*. The occurrence of DLT attributable to ofatumumab in $\leq 17\%$ serves as the boundary for the maximally tolerated dose (MTD) of ofatumumab.

Phase I trial procedures and analysis:

The initial group of 3 patients will be enrolled in the cohort 1. Dose escalation of ofatumumab will proceed according to the following: If no DLT is observed among 3 patients in a cohort, the next group of 3 will be treated at the next highest dose level. If the current level (i.e., the level at which no DLTs are observed) is the highest dose

level, three additional patients will be enrolled (total of six). If one DLT is observed among 3 patients in a cohort, the next group of 3 will be treated at this same dose level. If no more DLT is observed among the 3 additional patients (i.e. one DLT in total is observed among the 6 patients), then the next 3 patients will be treatment at the next highest dose level. If at least 1 more DLT is observed among the 3 additional patients, then the MTD is exceeded. If 6 patients have been treated at the next lower dose level, it will be considered as the MTD. If not, three additional patients will be enrolled. This escalation approach will then be continued until a dose is identified where at most 1 of 6 patients has a DLT. That dose will be considered to be the MTD. If two DLTs are observed among 3 (or fewer) patients in a cohort, the next group of 3 will be treated at the next lowest dose level. If the current level (i.e. the level at which 2 DLTs are observed) is the lowest dose level (300mg days 0 and 14), then a dose level -1 will be pursued, in which a de-escalated dose of 100mg ofatumumab will be given on days 0 and 14.

The total number treated on the phase I component will depend on the occurrence of dose limiting toxicity (DLT), however the maximal number accrued on the phase I study would approximate 12 to 18 total subjects. GSK reviewed phase I data prior to moving forward with the phase II component.

Phase II component:

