An early stopping rule for toxicity is constructed to continuously monitor the rate of DLT (i.e. grade 4 AE attributable to ofatumumab per the above definitions) for the 38 patients in a Phase II component. The DLT is defined in Section V.1. Safety. The stopping boundaries for monitoring the DLT is constructed as a Pocock-type boundary as described in “Continuous Toxicity Monitoring in Phase II Trials in Oncology” by Ivanova, Qaqish, and Schell (Biometrics, 2005; 61(2):540-45). Table below shows the number of DLTs allowed for a given number of “assessable” patients up to that point. Patients are considered to be “assessable” when they have either experienced a DLT or completed the surveillance period (death without a DLT or 30 days after infusion of Ofatumumab) without having experienced a DLT so that their outcomes are identifiable. Up to 20% of DLT rate is expected or acceptable. The table below contains the stopping boundaries for toxicity, based on which the probability of early stopping is at most 0.05 if the DLT rate is equal to 6.5%. Given the first 6 patients on the phase II component were treated on the phase I component of the trial (and assessed for DLT in the phase I component), the starting number of sequentially enrolled patients for assessment of this toxicity stopping boundary in the phase II component of the trial has been modified (see below table). When the DLT rate is unacceptably high (30%), the stopping rule has greater than 97% probability of early stopping. If a stopping boundary is reached, the accrual will be halted, and the data will be reviewed by the Moffitt Cancer Center Protocol Monitoring Committee.

# Assessable	Stopping boundaries for DLT	# Assessable	Stopping boundaries for DLT
1	NA	20	5
2	NA	21	5
3	NA	22	5
4	NA	23	5
5	NA	24	5
6	NA	25	5
7	NA	26	6
8	3	27	6
9	3	28	6
10	3	29	6
11	3	30	6
12	4	31	6
13	4	32	6
14	4	33	7
15	4	34	7
16	4	35	7
17	4	36	7
18	4	37	7
19	5	38	7

* These stopping boundaries apply to both the MTD cohort patients from the phase I component that move forward to the phase II trial, as well as those patients enrolled initially in the phase II component of the trial

* If these stopping boundaries are met, accrual will be suspended and the data will be reviewed in detail by the Protocol Monitoring Committee (PMC). The study will not be terminated, however. Resumption of accrual will be dictated by the review of the data by the study investigators and the PMC.

VII. DATA AND SAFETY MONITORING:

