ofatumumab. Liver chemistries consist of ALT, AST, total bilirubin, and alkaline phosphatase. Patients will have liver function tests performed before study therapy. Study patients will have liver function tests performed at least at each study visit. Patients with elevated liver function tests due to chronic GVHD are eligible. Grade 4 hepatic toxicity attributable to ofatumumab will inform the determination of dose-limiting toxicity in the phase I component of the study. In the phase II component, ongoing monitoring of AEs will capture any grade 4 hepatic toxicity attributable to ofatumumab, and review of these AEs will ensure patient safety.

Liver interruption/stopping criteria:

- Liver chemistry stopping and follow up criteria has been designed to assure subject safety and to evaluate liver event etiology. The sponsor-investigator is to review all events which meet liver chemistry stopping criteria to determine if the event was due to:

- tumor lysis (this is not likely in this study, as relapse of primary malignancy is an exclusion criterion), disease related liver involvement, or specifically hepatic chronic GVHD
- concomitant chemotherapy (or other medications)
- other identified cause and to exclude drug induced liver injury (DILI) due to Ofatumumab

These criteria are relevant for Ofatumumab studies because transient elevations in LFTs may be due to disease related liver involvement (particularly hepatic chronic GVHD in this study) or due to other chemotherapy (or other medication insults) rather than drug induced liver injury from Ofatumumab.

If the event is determined to be due to causes other than Ofatumumab DILI and improvement is observed after withdrawal of Ofatumumab, rechallenge may be attempted if deemed appropriate by the sponsor-investigator and in addition to consent of the subject.

Oncology Ofatumumab Protocols Liver Interruption/Stopping Criteria:

1. ALT >3 times upper limit of normal (ULN) **and** bilirubin >2 times ULN (>35% direct bilirubin; bilirubin fractionation required[‡])
2. ALT >8 times ULN
3. ALT >5 times ULN for more than 2 weeks

‡ NOTE: *If serum bilirubin fractionation not immediately available, study drug should be discontinued if ALT > 3xULN and bilirubin >2xULN. Serum bilirubin fractionation should be performed if testing is available. If testing unavailable, record presence of detectable urinary bilirubin on dipstick, indicating direct bilirubin elevations and suggesting liver injury.*

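### The phase II toxicity boundary describes the DLT as a grade 4 event, which contradicts Section V.1, where a grade 3 organ toxicity is a DLT

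*Combined protocol and SAP*

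**What the plan says.** Section V.1.a is headed "Definition of DLT for phase I component". Its item (c) counts as a DLT "Grade 3 organ toxicities (neurologic, pulmonary, cardiac, gastrointestinal, genitourinary, hepatic, cutaneous) at least possibly due to ofatumumab". The only exclusion by grade in V.1.a is for infusion-associated events of grades 1 to 3. Other grade 3 organ events count, subject to the exclusions by cause in item v.

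Section VI sends phase I counting to that definition ("above section V.1 safety for definition of DLT"). The Early Stopping Rule for Toxicity then says it will "continuously monitor the rate of DLT (i.e. grade 4 AE attributable to ofatumumab per the above definitions", and its next sentence reads "The DLT is defined in Section V.1. Safety". It adds: "When the DLT rate is unacceptably high (30%), the stopping rule has greater than 97% probability of early stopping".

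The liver monitoring text in Section VII also speaks of grade 4. For phase I: "Grade 4 hepatic toxicity attributable to ofatumumab will inform the determination of dose-limiting toxicity in the phase I component of the study". For phase II: "ongoing monitoring of AEs will capture any grade 4 hepatic toxicity attributable to ofatumumab".

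Reaching the boundary suspends accrual for review by the Protocol Monitoring Committee. The footnote to the table says the study is not terminated.

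**The concern.** The boundary counts events one at a time: 3 DLTs among 8 to 11 assessable patients, rising to 7 among 33 to 38. One or two events classified differently can decide whether accrual pauses. The sentence that introduces the boundary restates the DLT as a grade 4 event, and 'i.e.' marks a restatement, not an example. Someone classifying a phase II grade 3 pulmonary or hepatic event from that sentence would leave it out, although V.1(c) counts it. The boundary could then fail to trigger at a DLT rate that the protocol itself calls unacceptably high.

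**Working it through.** **Which definition is meant**

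- V.1(c): grade 3 organ toxicity is a DLT, with hepatic among the listed organs.
- Early Stopping Rule, first sentence: the DLT is a grade 4 event.
- Early Stopping Rule, next sentence: the DLT is the one in V.1. The Safety part of V.1 contains only one DLT definition, so the pointer can lead nowhere else.
- Early Stopping Rule, table footnote: the boundaries apply both to the MTD patients carried over from phase I, who were assessed under V.1, and to patients who enter in phase II. One cumulative count over 38 patients makes sense only with one definition.

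The grade 4 phrase is therefore the part that is wrong.

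**What the boundary does**

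Inputs, all from the Early Stopping Rule: no boundary at 1 to 7 assessable patients; then b(n) = 3 at 8–11, 4 at 12–18, 5 at 19–25, 6 at 26–32 and 7 at 33–38.

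Let P(n,k) be the probability of k counted DLTs after n patients with no boundary yet reached, and p the counted DLT rate:

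P(n,k) = P(n−1,k)·(1−p) + P(n−1,k−1)·p, starting from P(0,0) = 1.

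At each n, the mass with k ≥ b(n) is added to the stopping probability and removed.

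*The plan's own figure.* At p = 0.30 the result is 0.9787, which agrees with the stated figure of more than 97%. If stopping required exceeding b(n), the result would be 0.9413, so the table is an at-or-above rule. At p = 0.065 the result is 0.0547, slightly above the stated maximum of 0.05; that is a separate small matter.

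*The grade 4 wording.* Suppose the V.1 DLT rate is 30%, and a share f of the patients with a DLT have only a grade 3 organ event. The counted rate is then 0.30 × (1 − f). The documents give no value for f, so 0, one quarter and one half are assumed.

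| f | Counted rate | Chance of reaching the boundary | Same, given at most 1 DLT in the first six |
|---|---|---|---|
| 0 | 0.30 | 0.9787 | 0.9539 |
| 1/4 | 0.30 × 0.75 = 0.225 | 0.8577 | 0.7804 |
| 1/2 | 0.30 × 0.50 = 0.15 | 0.4935 | 0.3935 |

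The last column reflects that the first six patients come from the MTD cohort, which by the 3+3 rule has at most 1 DLT in 6. The loss from the full count is 0.9787 − 0.8577 = 0.1210, about 12 points, or 0.9787 − 0.4935 = 0.4852, about 49 points.

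**The case against.** The strongest reply is that the phrase is harmless shorthand. It says that it follows the definitions above, and the next sentence names V.1. Three of the four V.1 items (a, b and d) are grade 4, and grades 3 to 5 are collected to study day 60 apart from events directly attributable to chronic GVHD or relapse. The reply is right about intent. It does not make the restatement correct: the phrase equates the DLT with a grade 4 event, and the pointer leads to a heading limited to phase I. Collecting a grade 3 event is also not the same as counting it toward the boundary.

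A reader might infer more than the documents support:

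- *That phase II deliberately uses a narrower DLT.* No section says so, and the pointer and the shared count speak against it. If grade 4 were the intended event, the 30% would itself be a grade 4 rate and the stated figure of more than 97% would stand.
- *That grade 3 hepatic DLTs drop out of the 3+3.* The liver text says that grade 4 events inform the phase I determination; it does not say that grade 3 events do not. Phase I counting is sent to V.1. The phase II liver sentence concerns capturing adverse events, not counting them for the boundary. Both sentences misdescribe V.1(c), but neither overrides it.
- *That harm is missed at lower DLT rates.* With a grade 4 rate of 6.5% and grade 3 organ DLTs adding 5 or 10 points (both assumed), the chance of reaching the boundary is 5.5% on the grade 4 wording and 27% or 59% on V.1. The totals, 11.5% and 16.5%, lie below the 20% that the protocol calls acceptable, so fewer pauses there are not a missed unacceptable rate.

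**Conclusion.** Wrong as written, and minor. The Early Stopping Rule misstates the DLT that it counts; V.1 is clearly intended. If the grade 4 wording were followed at a V.1 DLT rate of 30%, the chance of reaching the boundary would be 86% with a quarter of DLTs uncounted and 49% with half uncounted, against 97.9% with all counted. Given at most 1 DLT in the first six, the corresponding figures are 78%, 39% and 95%. The drop rests on the assumed share of grade 3 organ events and on taking 30% as a V.1 rate; with no such events the two wordings give the same count. The liver monitoring sentences should be aligned for consistency, but they do not by themselves show that hepatic DLTs are miscounted.

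**What to change.** 1. Early Stopping Rule for Toxicity: replace the parenthesis with *as defined in Section V.1*.
2. V.1(c): change *Grade 3* to *Grade 3 or higher*. The item prints only grade 3, so once the grade 4 phrase is deleted, grade 4 organ toxicity has to be covered explicitly for every listed organ.
3. Liver monitoring, phase I and phase II sentences: replace *grade 4 hepatic toxicity* with *hepatic toxicity meeting V.1(c)*.
4. V.1.a heading: extend it to the phase II boundary, and state the surveillance window for that boundary. V.1 uses 46 days from the last dose, while the Early Stopping Rule treats a patient as assessable 30 days after infusion. Retitling alone would bring the two into direct conflict.

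These are wording changes, with no added patients, visits or analyses. The downside is that accrual may pause more often than under the grade 4 wording, sometimes at DLT rates below the 20% that the protocol accepts. Each pause leads to committee review, not termination.

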In a phase I/II study of escalating dose ofatumumab (300mg, 700mg or 1,000mg delivered on days 0 and 14) for rheumatoid arthritis (RA) patients who had failed prior disease modifying (DMARD) therapy, the study therapy was generally well tolerated. Part A was a double-blind, placebo-controlled, dose escalation study with randomized treatment allocation within each of 3 sequential dose cohorts. Subjects received 2 infusions on Day 0 and Day 14 of either ofatumumab (300 mg: n=12; 700 mg: n=10; 1000 mg: n=10) or placebo (n=7) and were followed for safety, efficacy, and PK measurements for 24 weeks. Part B was a double-blind, placebo-controlled parallel group study with randomization (1:1:1:1) into 1 of 4 treatment arms. Subjects received 2 infusions on Day 0 and Day 14 of either ofatumumab 300 mg (n=58), 700 mg (n=57), 1000 mg (n=54), or placebo (n=56) and were followed for safety, efficacy, and PK measurements for 24 weeks. In addition, following implementation via a protocol amendment, efficacy data, selected safety data (B cells, immunoglobulins, and SAEs) and samples for HAHA analysis were collected at Weeks 36 and 48. Pre-medication with corticosteroids was not initially required; however, based on severe infusion-related reactions reported during Part A and Part B, the protocol was amended to include pre-medication with corticosteroids, an additional dose of antihistamine, and an increased infusion volume and infusion time.

A total of 214 AEs in 37 subjects were reported in Study 403 Part A. The most frequently reported AEs were nausea, fatigue, urticaria, hypotension, rash, pyrexia, vomiting, diarrhea, chills, dyspnea, headache, hyperhidrosis, and leukocyturia. A total of 164 AEs were reported in the ofatumumab treatment groups; these AEs were generally of mild or moderate intensity, while 7% (12 events) were severe and one was life-

threatening (anaphylactoid-like reaction). Adverse events judged as related to study product were mainly infusion-related and were also those most frequently reported. The most frequent symptoms reported on an infusion day were rash, urticaria, and hypotension. Of the AEs reported in the ofatumumab groups, 79/164 (48%) were reported on an infusion day. Among these, AEs were reported with substantially higher frequency on the first infusion day (74/79, 94%) compared with the second infusion day, with no evidence of a dose effect.

MedDRA Preferred term	Placebo (N=7)		Ofatumumab Dose						Total (N=39)	

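### The toxicity rule's stated false-stopping limit of 0.05 is not a property of the written rule: the printed table gives 5.47%, and the assessable count adds a modest excess that depends on accrual

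*Combined protocol and SAP*

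**What the plan says.** Section VI, Early Stopping Rule for Toxicity, sets up continuous DLT monitoring "for the 38 patients in a Phase II component", with limits "constructed as a Pocock-type boundary". The table is indexed by the number of assessable patients. Patients reach that status "when they have either experienced a DLT or completed the surveillance period (death without a DLT or 30 days after infusion of Ofatumumab".

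Two operating characteristics are claimed. The first is that "the probability of early stopping is at most 0.05 if the DLT rate is equal to 6.5" percent. The second reads: "When the DLT rate is unacceptably high (30%), the stopping rule has greater than 97% probability of early stopping".

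The six patients treated at the MTD in phase I belong to the 38 and are already assessed. The adjustment to the table's starting row is explained by the clause "Given the first 6 patients on the phase II component were treated on the phase I component of the trial". Under the 3+3 rules in the same section, that cohort can carry at most 1 DLT in 6. Meeting a boundary suspends accrual for review by the Protocol Monitoring Committee and does not end the study. The documents give no accrual rate, no distribution of DLT onset and no allowance for assessment lag.

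**The concern.** A patient with a DLT joins the count on the day it occurs. A patient treated earlier and still free of DLT joins only when surveillance ends. While accrual continues, the numerator therefore holds every DLT so far and the denominator omits DLT-free patients still being watched.

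An example from the printed table: seven patients are assessed with 1 DLT. Patients 8 to 12 are then treated within 30 days, and patients 8 and 12 have a DLT on the infusion day. By the assessable count there are 7 + 2 = 9 patients and 3 DLTs. The boundary at 9 is 3, so accrual stops. In treatment order there are 2 DLTs at rows 8 to 11 (boundary 3) and 3 at row 12 (boundary 4), so it does not.

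At stake are the accuracy of a stated error probability and some avoidable suspensions of a regimen whose DLT rate is at the reference level.

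**Working it through.** **Inputs.** Boundary b(n) from the table: none for n = 1–7; 3 for 8–11; 4 for 12–18; 5 for 19–25; 6 for 26–32; 7 for 33–38. Reference DLT rate p = 6.5%, high rate 30%, 38 patients, of whom 6 are carried forward and 32 are new.

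**Step 1: the plan's own figures, no lag.** Let f(n,k) be the probability of k DLTs among the first n patients without an earlier crossing. Then f(n,k) = (1 − p)·f(n−1,k) + p·f(n−1,k−1). At each n the mass at or beyond the boundary is removed and added to the stopping probability.

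| Reading of the table | p = 6.5% | p = 30% |
|---|---|---|
| Stop when DLTs reach b(n) | 5.47% | 97.9% |
| Stop when DLTs exceed b(n) | 1.1% | 94.1% |

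The introductory sentence, "Table below shows the number of DLTs allowed for a given number of" assessable patients, could suggest the second reading. Only the first agrees with the claim of more than 97% at 30%, so I use it. The power claim then reproduces. The 0.05 claim is missed by about half a point, and the table gives exactly 5% at p = 6.31%.

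**Step 2: add the lag.** Simulation with the six phase I patients fully assessed beforehand and their DLT count drawn at 6.5%. The 32 new patients arrive by Poisson accrual. DLT patients enter the count at onset, and DLT-free patients at the end of the wait. Accrual rate and onset timing are assumptions. The plan does not say which infusion starts the 30 days, so I show 30 days and 14 + 30 = 44 days. Suspension probability at p = 6.5%:

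| Wait, DLT onset | 1/month | 2/month | 3/month |
|---|---|---|---|
| 30 days, uniform | 5.9% | 6.3% | 6.8% |
| 30 days, all on day 0 | 6.3% | 7.2% | 8.2% |
| 44 days, uniform | 6.1% | 6.7% | 7.4% |
| 44 days, all on day 0 | 6.7% | 8.2% | 9.7% |

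With a 30-day wait, the lag adds about 0.4–0.8 point at 1 per month and 0.9–1.7 points at 2 per month. It adds essentially nothing if patients are evenly spaced at 30 days or more, or if DLTs come at the end of the window. At p = 30% the stopping probability stays at about 98%.

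**Step 3: condition on the phase I cohort.** At p = 6.5%, P(0/6) = 0.935^6 = 0.668 and P(1/6) = 6 × 0.065 × 0.935^5 = 0.279. Without lag the recursion gives 1.43% from 0/6 and 8.12% from 1/6.

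- Weights over the two admissible states: 0.668/0.947 = 0.706 and 0.294.
- Average: 0.706 × 1.43 + 0.294 × 8.12 = 3.40%.
- Contribution of these states to the unconditional figure: 0.668 × 1.43 + 0.279 × 8.12 = 3.22 points. The other 5.47 − 3.22 = 2.25 points come from two or more DLTs in the six, which the 3+3 rule would not carry forward.

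With lag, over the same grid of rates, waits and onset patterns, the figure is about 1.5–3.5% from 0/6 and about 9–16% from 1/6. The average over the two states, with a 30-day wait and every DLT on day 0, is 4.1% at 1 per month and 4.9% at 2 per month.

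**The case against.** A reader might infer that the assessable count is what takes false suspension above 5%. The documents do not support that. The table already gives 5.47% with no lag, so entry in treatment order would not restore the stated limit. Since the table meets 5% at 6.31%, that half point is close to what rounding of the reference rate could produce.

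A reader might also infer that this trial would exceed 5% in practice. Given at most 1 DLT in the six carried-forward patients, the average is 3.4% without lag. It passes 5% only with faster accrual, or with the longer wait and early DLTs. From 0/6, about 70% of the admissible cases at this rate, it stays well below 5%.

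The larger lag figures rest on early onset. The background report that "AEs were reported with substantially higher frequency on the first infusion day (74/79, 94"%) covers infusion-day adverse events of any grade in the arthritis study's Part A. As a share of all 164 events in the ofatumumab groups, 74/164 is 45%. Section V.1 excludes grade 1–3 infusion events from DLT and includes grade 4 neutropenia lasting more than 14 days, which cannot be established on day 0. All DLTs on day 0 is therefore an upper bound.

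Finally, the section mentions sequential enrolment when it explains the table's starting row, which leaves some room for an enrolment-order reading. Counting known DLTs at once is a defensible cautious choice, and the committee can take pending patients into account.

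All of this stands, and it limits the size of the point. It does not make the 0.05 claim correct for the 38-patient rule as written, and it leaves the 1/6 start state at 8.1% before any lag.

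**Conclusion.** The point holds as a minor one. For the 38-patient rule, the stated limit of 0.05 is 5.47% by exact calculation. The assessable definition raises it to about 5.9–6.8% (uniform onset, 30 days) or 6.3–8.2% (all on day 0, 30 days), and to about 9.7% at most with a 44-day wait. The exact figure rests on suspension when DLTs reach the boundary. The lag figures rest also on assumed Poisson accrual of 1 to 3 patients per month.

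The single figure also hides a wide spread by start state: 1.4% from 0/6 and 8.1% from 1/6 without lag. Which of these applies is known once phase I ends. The consequence is limited to suspension for review. Detection of a 30% DLT rate is essentially unaffected by the lag, so this is not a gap in safety monitoring.

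**What to change.** Replace the 0.05 claim with the operating characteristics of the rule as written: the exact no-lag figures, plus a simulation at the expected accrual rate with its onset assumption stated. Report them separately for 0/6 and 1/6 DLTs in the carried-forward cohort, at 6.5% and at 30%. Averaged over the two states, the no-lag figure at 30% is 95.4%, so the 97% claim also needs this breakdown. State that accrual is suspended when DLTs reach the tabled number, and which infusion starts the surveillance period. The cost is a short calculation, a few sentences and a less favourable printed figure.

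Optionally, the sponsor may state that the table is entered in order of first infusion, with patients under surveillance holding their place. This removes the lag component only and leaves 5.47%. Its price is later suspension on some paths, so it is a trade-off for the sponsor and the committee to weigh.

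### The phase II toxicity rule scores a patient DLT-free 30 days after an unnamed infusion, 16 or 30 days before the DLT window it adopts has closed, and does not say how later DLTs count (minor)

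*Combined protocol and SAP*

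**What the plan says.** The Early Stopping Rule for Toxicity in Section VI monitors DLTs continuously in 38 patients, six of them carried over from phase I. It names its event by reference: "The DLT is defined in Section V.1. Safety". Section V.1.a opens its list with "Events occurring within 46 days of the last dose of drug (4 half-lives) that are" and then sets out the qualifying toxicities.

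A patient enters the boundary table on having a DLT, or on having "completed the surveillance period (death without a DLT or 30 days after infusion of Ofatumumab"). The rule adds that this second route must be passed "without having experienced a DLT so that their outcomes are identifiable". Two infusions are planned, on days 0 and 14, and the rule does not say which one starts the 30 days. It also does not say what happens if a patient already entered as DLT-free later has a V.1 DLT.

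Two other places bear on this. The DLT definition in the phase I part of Section VI also gives 46 days, but counts them from the start of ofatumumab. Section VII requires grade 3-5 adverse events to be collected to study day 60, except those directly attributable to chronic GVHD or to relapse.

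The rule claims a stopping probability of at most 0.05 at a 6.5% DLT rate and above 97% at 30%. A crossing suspends accrual for Protocol Monitoring Committee review; the study is not terminated.

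**The concern.** The surveillance period exists so that each patient's outcome is known when it enters the table. At day 30 or day 44 the V.1 outcome is not yet known. One listed DLT shows this: grade 4 neutropenia must last more than 14 days, so neutropenia that starts more than 16 days after the reference infusion cannot qualify within 30 days (30 - 14 = 16).

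A continuous boundary needs its numerator and denominator to describe the same event over the same period. Here the denominator can advance before the numerator is final, and the correction for a late event is left unwritten. Whether accrual pauses could then depend on a decision made after the event is seen. The stated stopping probability at 30% also holds only if late events are counted.

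**Working it through.** **Windows, in study days**

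| Source | Calculation | Closes | Days before V.1 closes |
|---|---|---|---|
| V.1.a, 46 days from last dose | 14 + 46 | 60 | 0 |
| Stopping rule, from second infusion | 14 + 30 | 44 | 16 |
| Stopping rule, from first infusion | 0 + 30 | 30 | 30 |
| Section VI phase I text, 46 days from initiation | 0 + 46 | 46 | 14 |

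**Reproducing the plan's figure.** The printed table has no boundary below 8 assessable patients. It is then 3 at 8-11, 4 at 12-18, 5 at 19-25, 6 at 26-32 and 7 at 33-38. Let P(n, k) be the probability of reaching patient n with k DLTs and no earlier stop. Then P(n, k) = P(n-1, k)(1 - p) + P(n-1, k-1)p, and any mass with k at or above the boundary is removed as stopped. With p = 0.30 for all 38 patients, the total stopped is 0.979. This agrees with the stated figure of more than 97%.

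**Late DLTs never added.** Keep patients 1-6 at 0.30. Set patients 7-38 to 0.30 × s, where s is the share of their DLTs that falls before the cut-off. The documents do not give s, so a range is assumed.

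| s | Counted rate, patients 7-38 | P(stop) at a true 30% |
|---|---|---|
| 1.00 | 0.300 | 97.9% |
| 0.95 | 0.285 | 97.0% |
| 0.90 | 0.270 | 95.8% |
| 0.80 | 0.240 | 92.4% |

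**Late DLTs added when they occur.** This was simulated with 20,000 trials per setting. The six phase I patients were complete and 32 phase II patients entered at 1 or 2 a month. The DLT rate was 30%, with 10% or 20% of DLTs spread evenly between the cut-off and day 60.

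- 30-day cut-off, late DLTs added: P(stop) 98.0-98.2%.
- Surveillance to day 60: P(stop) 98.1-98.5%.
- Mean enrolment at the halt differed by 0.01 to 0.11 patients.

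**Sensitivity to the six carried-over patients.** They reach phase II only if at most 1 of 6 had a DLT. Conditioning on that, P(stop) at 30% is 95.4% with every DLT counted.

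**The case against.** The strongest reply is that the rule already works. A patient is assessable on having experienced a DLT, and that clause carries no day limit. Monitoring is continuous, and the adverse event data run to day 60. On that reading a late DLT is simply added, and the simulation shows almost no loss. Harm arises only if the committee leaves a recorded DLT out of the count. This stands as an argument about size. It does not settle the wording: nothing says that a patient entered as DLT-free is re-scored, and the two planned infusions leave the cut-off itself ambiguous.

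A reader might infer that the plan's claim of more than 97% is wrong, or that it breaks once about 5% of DLTs are missed. The documents do not support either. The late share is unknown, the loss vanishes if late events are added, and the 5% point depends on giving the six carried-over patients an unconditional 30% rate. Conditioned on their phase I result, the probability is below 97% whichever window is used.

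A reader might also infer from the gloss "rate of DLT (i.e. grade 4 AE attributable to ofatumumab per the above definitions") that phase II monitors grade 4 events only, which would leave out V.1's "Grade 3 organ toxicities (neurologic, pulmonary, cardiac, gastrointestinal, genitourinary, hepatic, cutaneous) at least possibly due to ofatumumab". The gloss points back to the earlier definitions and the next sentence adopts V.1, so V.1 probably governs, although V.1.a is headed "Definition of DLT for phase I component". This is a question for the sponsor, not a demonstrated second endpoint.

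**Conclusion.** The mismatch is real and minor. The rule adopts a DLT whose window closes on day 60 and scores patients DLT-free on day 44 or day 30. It is a conflict between a stated cut-off and the definition it uses, rather than only a missing detail.

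Its effect depends on one unstated counting rule. With late DLTs added, the effect is negligible. With late DLTs left out, the loss in stopping probability at a true 30% rate is about 2 points if 10% are late (97.9 - 95.8 = 2.1) and 5 to 6 points if 20% are late (97.9 - 92.4 = 5.5). These figures rest on the assumed shares, on stopping when the count reaches the printed boundary, and on the unconditional 30% for the carried-over patients.

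The response-rate analysis is untouched, and no effect on the phase I escalation decisions is claimed.

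**What to change.** 1. In the Early Stopping Rule for Toxicity, end the surveillance period 46 days after the last dose of ofatumumab. Add one sentence: any V.1 DLT within that window counts whenever it occurs.
2. In the phase I DLT definition in Section VI, count the 46 days from the last dose instead of from initiation, to match V.1.a.
3. Confirm whether the 6.5%, 20% and 30% rates describe V.1 DLTs, including grade 3 organ toxicities. If they do, remove the grade 4 gloss and keep the table. If they do not, set rates for V.1 DLTs and recompute the table before removing the gloss.

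Items 1 and 2 cost wording only, since grade 3-5 events are already collected to day 60. The downside is that DLT-free patients become assessable 16 or 30 days later. At a 30% rate this added 0.01 to 0.11 patients to mean enrolment at the halt in the simulation, compared with the present cut-off and late DLTs added.
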